**Clinical symptom score outcome and response:**

Clinical outcome and response will be programmatically determined by comparing the scores of the signs and symptoms at each visit to those present at baseline. The detailed definitions are provided in Appendix 7.

**Main analytical approach**

- Frequency and percentage of participants in each outcome and response category of the investigator’s assessment of clinical resolution response at Day 2 through Day 6 (when collected and as data permit), ToC and follow-up visits will be summarized along with 95% Clopper-Pearson CI by treatment group.
- Frequency and percentage of participants in each outcome and response category of clinical symptom score at Day 2 through Day 6 (when collected and as data permit), ToC and follow-up visits will be summarized along with 95% Clopper-Pearson CI by treatment group.
- Frequency and percentage of participants for each individual clinical symptom score (four individual clinical symptoms, each with four possible scores (ordinal categories)) will be summarised by visit and treatment group
- Total clinical symptom score over time will be summarized graphically in boxplots by visit and treatment group

CCI

#### 4.4.6. Quantitative bacteriology culture results

- Bacteriology culture results categories (No Growth ( $<10^3$ ),  $\geq 10^3 - <10^4$ ,  $\geq 10^4 - <10^5$ ,  $\geq 10^5$ , Indeterminate)
- Quantitative bacteriology culture results will be summarized by counts and percentages for each category by visit for Micro-MPP CCI analysis sets for each treatment arm.
- Number of participants in each bacteriology culture result category for each visit will be summarized graphically for Micro-MPP CCI analysis sets for each treatment arm.

CCI

CCI

CCI

## 4.5. Safety Analyses

All safety analysis will be performed on the Safety analysis set and presented by treatment group and presenting combined cohorts (Cohort1 + Cohort 2), unless otherwise specified. Safety secondary endpoints are defined in Section 4.3.2 and estimand for safety are provided in the Section 1.1.2.

### 4.5.1. Extent of Exposure

Exposure to study treatment and compliance will be summarised descriptively overall and by cohort. Details of the derivations will be included in the OPS.

### 4.5.2. Adverse Events

An adverse event (AE) is considered on-intervention if the AE onset or worsening is on or after study intervention start. All AE summaries will present on-intervention events unless otherwise specified. SAE summaries will be based on all SAEs reported regardless of whether they meet the definition of on-intervention or not.

Adverse events will be coded using the standard Medical Dictionary for Regulatory Activity (MedDRA) and graded by the investigator according to Division of Microbiology and Infectious Diseases Adult Toxicity Tables for Adverse Event Assessment (see Protocol Section 10.7).

The following summary tables will be presented:

- AEs by SOC and PT and maximum intensity
- SAEs by SOC and PT and maximum intensity
- Common ( $\geq 10\%$ ) AEs
- Study intervention-related\* AEs by SOC and PT and maximum intensity
- Study intervention-related\* SAEs by SOC and PT and maximum intensity
- Study intervention-related\* Common AEs ( $\geq 10\%$ )
- Common ( $\geq 10\%$ ) Non-serious Adverse Events by SOC and PT

\*A study intervention-related AE/SAE is defined as an AE/SAE for which the investigator classifies the relationship to study intervention as “Yes”.

#### 4.5.2.1. Adverse Events of Special Interest

There are no adverse events of special interest in this study.

### **4.5.3. Additional Safety Assessments**

#### **4.5.3.1. Laboratory Data**

Summary tables for laboratory data (haematology, clinical chemistry) will be produced:

- Change from baseline over time
- Frequency and percentage of laboratory results (relative to Normal Range) post-baseline relative to baseline
- Note: values of PCI will be flagged in listings only.

Separate summary tables for haematology and clinical chemistry laboratory tests will be produced. The following will be presented, at a minimum:

- Haematology parameters (including Platelet count, RBC count, Hemoglobin, Hematocrit, RBC Indices (Mean corpuscular volume (MCV), Mean corpuscular Hemoglobin (MCH), %Reticulocytes), WBC count (Lymphocytes, Neutrophils, Monocytes, Eosinophils, Basophils))
- Clinical chemistry parameters (including Blood urea nitrogen (BUN), Potassium, Sodium, Creatinine, Glucose(non-fasting), AST, SGOT, ALT, SGPT, Alkaline phosphatase, Total and direct bilirubin, calcium & Total Protein)

Additionally, summary tables for urinalysis data will be produced:

- Change from baseline in urine concentrations over time
- Frequency and percentage of urinalysis results post-baseline relative to baseline
- Note: values of PCI will be flagged in listings only.

The following will be presented, at a minimum:

- Urinalysis parameters (Specific gravity, pH, glucose, protein, blood, ketones, bilirubin, urobilinogen, nitrite, leukocyte esterase by dipstick. Microscopic examination (if blood or protein is abnormal), Protein/creatinine ratio)

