	
degeneration/ regeneration in the kidney. Other urinary tract findings included tubular dilatation, interstitial mononuclear cell infiltration, neutrophilic inflammation in the papilla and epithelial and urothelial hypertrophy/ hyperplasia of the papilla lining, pelvis and/or urinary bladder, respectively. In addition, there were increases in serum urea, creatinine, phosphorus and potassium and increased urinary protein and glucose excretion in rats given CCI mg/kg/day.
 
In a 26-week rat toxicity study, there was a slight increased incidence of tubule basophilia (graded as minimal) in the kidney of males at CCI mg/kg/day and increased incidence of hyaline droplet accumulation (graded as minimal) in the kidney tubular epithelium of males at <math>\geq</math> CCI mg/kg/day, both which may be an exacerbation of spontaneous changes. In the urinary bladder epithelium hypertrophy/hyperplasia was noted in of males at <math>\geq</math> CCI mg/kg/ day and females at <math>\geq</math> CCI mg/kg/day. At CCI mg/kg/day there was an increase in mean urine microalbumin and urine clusterin concentration (females only). Changes in urinary biomarkers and microscopic renal findings were considered
	

Potential Risk of Clinical Significance	Summary of Data/Rationale for Risk	Mitigation Strategy
	
fully recovered after 8 weeks off-dose, the urinary bladder changes at CCI mg/kg/day were still present after 8 weeks off-dose but occurred with decreased incidence suggesting partial reversal.
 
In a 14 day CCI toxicity study in dogs, minimal to slight degeneration/ regeneration was observed in the kidney with changes in clinical pathology parameters (increased serum urea nitrogen and creatinine) at doses <math>\geq</math> CCI mg/kg/day, these changes also correlated with clinical signs of dehydration as these dose levels were not considered tolerated.
 
In a 39-week toxicity study in dogs there was an increased incidence of non-adverse tubular degeneration/regeneration in males at <math>\geq</math> CCI mg/kg/day and in females at CCI mg/kg/day. These changes were not seen after the 8-week recovery period. Additionally, unclassified urinary crystals were noted in the urine microscopic evaluation of a few animals at CCI mg/kg/day, during the dosing period.
 
Clinical
 
During the FTIH (212148) study in healthy participants, there were no reports of any renal associated adverse events. In this
	

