## 10.7. Appendix 7: Division of Microbiology and Infectious Diseases Adult Toxicity Tables for Adverse Event Assessment

**ESTIMATING SEVERITY GRADE:** For abnormalities NOT found elsewhere in the Toxicity Tables, use the scale below to estimate grade of severity:

GRADE 1	Mild	Transient or mild discomfort (<48 hours); no medical intervention/therapy required
GRADE 2	Moderate	Mild to moderate limitation in activity – some assistance may be needed; no or minimal medical intervention/therapy required
GRADE 3	Severe	Marked limitation in activity, some assistance usually required; medical intervention/therapy required, hospitalizations possible
GRADE 4	Life-threatening	Extreme limitation in activity, significant assistance required; significant medical intervention/therapy required, hospitalization or hospice care probable

**SERIOUS OR LIFE-THREATENING AEs:** ANY clinical event deemed by the investigator to be serious or life-threatening should be considered a Grade 4 event. Clinical events considered to be serious or life-threatening include, but are not limited to: seizures, coma, tetany, diabetic ketoacidosis, disseminated intravascular coagulation, diffuse petechiae, paralysis, acute psychosis, and severe depression.

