### **COMMENTS REGARDING THE USE OF THESE TABLES**

- Standardized and commonly used toxicity tables (Division of AIDS, National Cancer Institute's Common Toxicity Criteria, and World Health Organization) have been adapted for use by the Division of Microbiology and Infectious Diseases (DAIDS) and modified to better meet the needs of participants in Division of Microbiology and Infectious Diseases (DMID) trials.
- For parameters not included in the following Toxicity Tables, study sites should refer to the "Guide for Estimating Severity Grade" located above.
- Criteria are generally grouped by body system.

Some protocols may have additional protocol-specific grading criteria, which will supersede the use of these tables for specified criteria.

**Note:** Adult DMID toxicity criteria will be applied for all laboratory parameters, with the exception of serum creatinine adolescent laboratory data, which will be assessed using pediatric DMID toxicity criteria. The DMID pediatric toxicity table may be accessed at <https://www.niaid.nih.gov/sites/default/files/dmidpedtox.pdf>.

HEMATOLOGY				
	Grade 1	Grade 2	Grade 3	Grade 4
Hemoglobin	9.5 to 10.5 gm/dL	8.0 to 9.4 gm/dL	6.5 to 7.9 gm/dL	<6.5 gm/dL
Absolute Neutrophil Count	1000 to 1500 /mm 	750 to 999 /mm 	500 to 749 /mm 	<500 /mm 
Platelets	75,000 to 99,999 /mm 	50,000 to 74,999 /mm 	20,000 to 49,999 /mm 	<20,000 /mm 
White Blood Cells	11,000 to 13,000 /mm 	13,000 to 15,000 /mm 	15,000 to 30,000 /mm 	>30,000 or <1000 /mm 
% Polymorphonuclear Leukocytes + Band Cells	>80%	90 to 95%	>95%	N/A
Abnormal Fibrinogen	Low: 100 to 200 mg/dL High: 400 to 600 mg/dL	Low: <100 mg/dL High: >600 mg/dL	Low: <50 mg/dL High: N/A	Fibrinogen associated with gross bleeding or with disseminated coagulation
Fibrin Split Product	20 to 40 mcg/mL	41 to 50 mcg/mL	51 to 60 mcg/dL	>60 mcg/dL
Prothrombin Time (PT)	1.01 to 1.25 × ULN	1.26 to 1.5 × ULN	1.51 to 3.0 × ULN	>3 × ULN
Activated Partial Thromboplastin (APTT)	1.01 to 1.66 × ULN	1.67 to 2.33 × ULN	2.34 to 3 × ULN	>3 × ULN
Methemoglobin	5.0 to 9.9%	10.0 to 14.9%	15.0 to 19.9%	>20%

N/A=not applicable; ULN=upper limit of normal.

CHEMISTRIES				
	Grade 1	Grade 2	Grade 3	Grade 4
Hyponatremia	130 to 135 mEq/L	123 to 129 mEq/L	116 to 122 mEq/L	<116 mEq/L or abnormal sodium with mental status changes or seizures

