## 2. STATISTICAL HYPOTHESES

No formal statistical hypotheses will be tested in this study.

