### 6.3. Appendix 3 Data Derivations Rule

#### 6.3.1. Criteria for Potential Clinical Importance

Reference ranges for all laboratory parameters collected throughout the study are provided by the laboratory. A laboratory value that is outside the reference range is considered either high abnormal (value above the upper limit of the reference range) or low abnormal (value below the lower limit of the reference range). Note: a high abnormal or low abnormal laboratory value is not necessarily of clinical concern.

In addition, the following criteria will be used to flag potential clinical importance:

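### Protocol 10.7 applies DMID criteria to all laboratory parameters, but the SAP plans no laboratory grade table, and its listing flags omit BUN, urine protein and urine blood

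*SAP*

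**What the plan says.** Protocol 10.7 prints DMID grades for haematology, chemistry, enzymes and urinalysis, with a note that "Adult DMID toxicity criteria will be applied for all laboratory parameters". The only exception is adolescent serum creatinine, which cannot arise because entry starts at 18 years.

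SAP 4.5.3.1 plans two summaries for haematology and chemistry: change from baseline over time, and "Frequency and percentage of laboratory results (relative to Normal Range) post-baseline relative to baseline". Urinalysis gets change from baseline and a frequency table of results, without reference to a normal range. In both blocks "values of PCI will be flagged in listings only". SAP 6.3.1 introduces the limits by saying that "the following criteria will be used to flag potential clinical importance", and 6.3.1.1 lists them for haematology, chemistry and liver tests.

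DMID appears in the SAP only in 4.5.2, where adverse events are "graded by the investigator according to Division of Microbiology and Infectious Diseases Adult Toxicity Tables for Adverse Event Assessment" and then tabulated by maximum intensity.

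**The concern.** Clinically significant laboratory change is part of a secondary endpoint, and the safety estimand in SAP 1.1.2 asks for frequencies and percentages. No planned laboratory table applies a severity threshold beyond the normal range. A BUN of 1.25 x ULN (the start of DMID Grade 1) and one of 5.1 x ULN (the start of Grade 3) fall in the same above-range cell.

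Renal change is a named potential risk. Protocol 2.3.1 reports "increases in serum urea, creatinine, phosphorus and potassium and increased urinary protein and glucose excretion" in a 13-week rat study, and the three DMID-graded panel tests with no PCI limit are all renal or urinary. Eligibility extends down to an eGFR of 60, and Cohort 2 is contacted only by telephone on Days 3 to 5, so the samples that are taken should be read as fully as possible.

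**Working it through.** No sample size or test is involved ("No formal statistical hypotheses will be tested in this study"), so the check compares limits line by line.

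**Coverage.** Counting high and low separately for sodium, potassium, glucose and calcium, 20 items graded in Protocol 10.7 belong to the Protocol Table 5 panel. SAP 6.3.1.1 sets a limit for 17, and 20 - 17 = 3 have none: BUN, urine protein and urine blood. SAP 4.5.3.1 promises urinalysis PCI flags, but 6.3.1 defines no urinalysis limit, so that flag cannot be programmed.

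**Where the flags start.** Splitting white cells into high and low turns the 17 items into 18 limits. Conversions: glucose mmol/L x 18.016 and calcium mmol/L x 4.008 give mg/dL; sodium and potassium in mmol/L equal mEq/L.

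| Parameter | DMID Grade 1 | SAP flag | Flag starts in |
|---|---|---|---|
| White cells, high | 11,000-13,000/mm³ | >15 x10⁹/L | Grade 3 |
| Sodium, low | 130-135 | <130 | Grade 2 |
| Sodium, high | 146-150 | >150 | Grade 2 |
| Potassium, low | 3.0-3.4 | <3 | Grade 2 |
| Glucose, low | 55-64 mg/dL | <3 mmol/L = 54.0 | Grade 2 |
| Glucose, high | 116-160 mg/dL | >9 mmol/L = 162.1 | Grade 2 |
| ALT, AST, ALP (three limits) | 1.1 to <2.0 x ULN | ≥2 x ULN | Grade 2 |
| Bilirubin | from 1.1 x ULN | ≥1.5 x ULN | Grade 2; Grade 3 if another liver test is raised |
| Calcium, low | 8.4-7.8 mg/dL | <2 mmol/L = 8.02 | inside Grade 1 |
| Calcium, high | 10.6-11.5 mg/dL | >2.75 mmol/L = 11.02 | inside Grade 1 |
| Haemoglobin, low | 9.5-10.5 g/dL | <10.0 | inside Grade 1 |
| Creatinine | 1.1-1.5 x ULN | >120 µmol/L | inside Grade 1 |
| Neutrophils, low | 1000-1500/mm³ | <1.5 x10⁹/L | matches |
| Platelets, low | 75,000-99,999/mm³ | <100 x10⁹/L | matches |
| Potassium, high | 5.6-6.0 | >5.5 | matches |
| White cells, low | none before Grade 4 (<1000/mm³) | <3 x10⁹/L | stricter than DMID |

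Ten limits start at Grade 2 or above and four start inside Grade 1, so 10 + 4 = 14 start later than DMID. Three match and one is stricter: 14 + 3 + 1 = 18.

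**Assumptions in the count.** The SAP gives haemoglobin in g/L, which would make the low limit 1.0 g/dL; I read it as g/dL. Taken literally it would fall in Grade 4, and the ten would become eleven. The creatinine ULN is not in the documents. Over an assumed 80 to 106 µmol/L, 120 is 120/106 = 1.13 to 120/80 = 1.50 x ULN. At 80 the flag sits at the very top of Grade 1, so creatinine counts as inside Grade 1 only for a ULN above 80.

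**The adverse event route.** Protocol 8.2.4 makes clinically significant laboratory changes adverse events, so these are graded and tabulated. The same section treats findings tied to the underlying disease as not clinically significant unless worse than expected. In a urinary infection trial, urine protein and blood are easily attributed to the infection; exclusion 28 itself sets aside transient proteinuria during infection. The route therefore filters these markers by investigator judgement.

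**The case against.** A reader might infer that the severity of laboratory changes is never reported. The documents do not support that. Changes judged clinically significant become adverse events, graded by DMID and tabulated by maximum intensity, and Protocol 2.3.1 has renal events recorded on the DMID scale. BUN, creatinine, urine protein, urine blood and the protein/creatinine ratio are all summarised. SAP 4.1.1 provides minima and maxima, and 6.3.4 displays the worst post-baseline value, so a large outlier would be visible. Dipstick protein is ordinal, and a frequency table of results may show the categories that DMID uses.

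Nor can one say that the PCI list replaces DMID with generally higher limits. It is a listing flag beside the tables, three limits match and one is stricter. Raised potassium, one of the animal signals, is flagged from the start of Grade 1.

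The strongest argument is that no grade table was ever promised. Appendix 7 is titled "Division of Microbiology and Infectious Diseases Adult Toxicity Tables for Adverse Event Assessment", its adolescent exception suggests template text, and Protocol 9.3.3 offers only descriptive statistics for laboratory parameters. The Output and Programming Specification, which is not available here, may add displays.

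Much of this stands and limits the size of the point. It does not remove it. The note in 10.7 is specifically about laboratory parameters, so if only adverse event grading was meant the note is wrong. The adverse event route is selective, and the undefined urinalysis flag is a gap on any reading.

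**Conclusion.** The mismatch is real but bounded. Protocol 10.7 and SAP 4.5.3.1 disagree on whether laboratory values are graded. Under the SAP, grades reach the tables only through reported adverse events. Three of 20 graded panel items have no PCI limit, and 10 of 18 comparable limits start at Grade 2 or above. The loss falls on laboratory changes that the investigator judges not clinically significant: they are summarised but ungraded. In a descriptive Phase 1b study this threatens no inference, but it weakens reporting on a secondary endpoint and a named risk, and it is cheap to correct.

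The counts rest on the haemoglobin unit and creatinine ULN assumptions above. I place no weight on the lack of a Table 2 entry beyond noting that no visible row records the point; part of that table is blacked out.

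**What to change.** In SAP 4.5.3.1, add a table of baseline against worst post-baseline DMID grade, by treatment group, for the Protocol Table 5 parameters that can be graded from collected data. Include BUN, creatinine, potassium, liver enzymes and dipstick urine protein, with high and low directions kept separate. State how three awkward items are graded, or that they are left out: calcium (DMID corrects for albumin, which is not in Table 5), bilirubin (the grade depends on other liver tests) and haematuria (grades need observation of gross blood or clots, and microscopy is conditional).

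Keep the existing PCI flags. Replacing them with DMID grades would lose haematocrit, lymphocytes, albumin, high haemoglobin, high platelets and white cells between 1 and 3 x10⁹/L. Add limits for BUN and urinalysis, and correct the haemoglobin unit.

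The cost is somewhat longer output and some derivation rules, such as how to treat creatinine between 1.5 and 1.6 x ULN. No new sampling is needed, and the worst post-baseline value is already derived.

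If the sponsor intends DMID for adverse events only, reconcile the sentence in Protocol 10.7 with the SAP, record that in SAP Table 2, and still add the missing flags.

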Renal Changes	
Nonclinical
 
Dogs given <math>\geq</math> CC1 mg/kg/day for 14 days had minimal to slight degeneration/ regeneration with changes in clinical pathology parameters (increased serum urea nitrogen and creatinine) which also correlated with clinical signs of dehydration as these dose levels were not considered tolerated.
 
In a 14-day CC1 toxicity study in rats, minimal to moderate tubule cell hypertrophy was noted in the kidney of animals given <math>\geq</math> CC1 mg /kg /day, slight tubule cell degeneration /necrosis of tubule cells was also noted in one
	
Dosing at a lower dose and for shorter duration than the regimen used in the FTIH study CC1 mg CC1 for a maximum of 5 days).
 
Standard clinical monitoring with elicitation of clinical symptoms; physical examinations and routine safety blood haematology, chemistry tests and urinalysis (Section 1.3).
 
Monitoring for AEs. Any renal event will be monitored and recorded for severity according to DMID (division of microbiology and infectious diseases) adult toxicity guidance (Section 10.7).
 
Monitoring of serum creatinine levels with follow up assessments obtained for any change from baseline <math>>1.5X</math> (Section 8.2.4.2)

Potential Risk of Clinical Significance	Summary of Data/Rationale for Risk	Mitigation Strategy

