### **8.2.4. Clinical Safety Laboratory Tests**

- See Section 10.2 for the list of clinical laboratory tests to be performed and the SoA for the timing and frequency.
- The investigator must review the laboratory report, document this review, and record any clinically significant changes occurring during the study as an AE. The laboratory reports must be filed with the source documents.
- Abnormal laboratory findings associated with the underlying disease are not considered clinically significant, unless judged by the investigator to be more severe than expected for the participant's condition.
- All laboratory tests with values considered clinically significantly abnormal during participation in the study or within 3 days after the last dose of study intervention should be repeated until the values return to normal or baseline or are no longer considered significantly abnormal by the investigator or medical monitor.
  - If clinically significant values do not return to normal/baseline within a period of time judged reasonable by the investigator, the etiology should be identified and the sponsor notified.
- In the absence of a diagnosis, abnormal laboratory findings assessments or other abnormal results the investigator considers clinically significant will be recorded as an AE or SAE, if they meet the definition of an AE or SAE (see Section 10.3.1 and Section 10.3.2).
- All protocol-required laboratory tests, as defined in Section 10.2, must be conducted in accordance with the laboratory manual and the SoA (Section 1.3).
- If laboratory values from non-protocol specified laboratory tests performed at the institution's local laboratory require a change in participant management or are considered clinically significant by the investigator (e.g., SAE or AE or dose modification), then the results must be recorded.

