**8.2.4.2. Management of participants with changes in serum creatinine**

Automatic lab alerts will be sent by the central lab to the investigator and Medical Monitor for increased levels of serum creatinine  $>1.5\times$  compared to baseline levels.

Upon receipt of the automatic lab alert, the investigator should perform:

- clinical assessment (e.g. symptoms improvement or deterioration)
- physical examination
- repeat lab tests (urinalysis, hematology and chemistry including any additional inflammatory markers) as a split sample (send to local and central lab)

Such assessments will be performed as soon as possible and may require participants to return to clinic as an unscheduled visit, if after clinic constrained intervention period for cohort 1 or a non-visit day for cohort 2.

This will also trigger case discussion between the investigator and Medical Monitor (e.g. by phone or email) to ensure assessments are initiated after the flag, to discuss status of the participant and additional appropriate management will be initiated by the investigator (e.g. no actions required, switch to daily monitoring, discontinue study medication, oral rehydration, or others).

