### 1.1.2. Estimand for Secondary Endpoints

The secondary clinical questions of interests are,

1. *What is the incidence of AEs, SAEs and clinically significant changes in safety data from baseline (laboratory, vitals and ECG) following CCI oral dosing for 5 days of GSK3882347 (or less than 5 days if study intervention is discontinued for any reason) in adult female participants with uUTI?*

The estimand is described by the following attributes:

- Population: Female participants with acute uUTI.
- Treatment condition: GSK3882347 CCI mg given orally CCI for 5 days or Nitrofurantoin 100mg given orally twice daily for 5 days.
- Variables:
  - Occurrence of adverse events (AEs) and serious adverse events (SAEs)
  - Clinically significant changes from baseline in laboratory values (haematology, chemistry and urinalysis), vital signs and 12 lead electrocardiogram (ECG) readings at each visit.
- Summary measure: Frequency and percentages for AEs, SAEs, laboratory values, vital signs and ECG values.
- Main intercurrent events anticipated:
  - Use of rescue medication - Treatment policy strategy
  - Discontinuation from the treatment due to any reason (withdrawal of consent /AEs (if not part of the endpoint definition, for example, in AE and SAE)/missed doses)-Treatment policy strategy

The interest lies in the full safety profile regardless of the occurrence of these intercurrent events. Hence safety data evaluated throughout the study will be considered for the analysis.

2. *To evaluate the plasma and urine PK concentrations following CCI oral dosing for 5 days of GSK3882347 or until discontinuation of treatment*

The estimand is described by the following attributes:

- Population: Female participants with acute uUTI
- Treatment condition: GSK3882347 given orally CCI for 5 days
- Variables:
  - Plasma:
    - GSK3882347 trough concentration on Day 1 and Day 5 (Ctau)
  - Urine:
    - Urine concentration at 22-24h collection following dose on Day 1 and Day 5
- Summary measure: Mean, 95% confidence interval (CI), standard deviation (SD), median, minimum, and maximum and geometric mean, 95% CI of geometric mean, and coefficient of variation (CV) of geometric mean, for log transformed data.
- Main intercurrent events anticipated:
  - Discontinuation from the treatment due to any reasons (AEs/withdrawal of consent/missed doses)
  - Administered incorrect dose based on adherence records

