#### 4.3.2. Safety

The following endpoints will be analysed:

- Occurrence of adverse events (AEs) and serious adverse events (SAEs)
- Clinically significant changes from baseline in laboratory values (haematology, chemistry and urinalysis), vital signs and 12-lead electrocardiogram (ECG) readings at each visit

Analysis of safety data will be conducted by using the Safety analysis set. Details on the safety estimand are given in Section 1.1.2. The details of the safety analyses are provided in Section 4.5.

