#### 4.5.3.3. ECG

Summary tables for ECG data will be produced:

- ECG findings
- Change from baseline in ECG values
- Maximum QTc values post-baseline relative to baseline by category
- Maximum increase in QTc values post-baseline relative to baseline by category
- Note: values of PCI will be flagged in listings only.

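### No visible SAP table or flag counts the protocol's own renal trigger (creatinine above 1.5 times baseline), and the SAP's absolute flag misses such rises when baseline is below 80 µmol/L and the value ends at or below 120

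*SAP*

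**What the plan says.** SAP 4.3.2 lists, beside adverse events, the endpoint "Clinically significant changes from baseline in laboratory values (haematology, chemistry and urinalysis), vital signs and 12-lead electrocardiogram (ECG) readings at each visit". For the same estimand SAP 1.1.2 gives: "Summary measure: Frequency and percentages for AEs, SAEs, laboratory values, vital signs and ECG values".

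The SAP does not define clinically significant. Its only numeric importance criteria are the PCI limits in 6.3.1, and 4.5.3.1 says of them: "Note: values of PCI will be flagged in listings only". The same note appears for urinalysis (4.5.3.1), vital signs (4.5.3.2) and ECG (4.5.3.3). For creatinine, 6.3.1.1 gives one PCI limit, an absolute high flag above 120 µmol/L.

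The SAP does plan tables. For blood tests it has change from baseline and "Frequency and percentage of laboratory results (relative to Normal Range) post-baseline relative to baseline". For ECG it has findings, maximum QTc by category and "Maximum increase in QTc values post-baseline relative to baseline by category". Adverse events are tabulated by system organ class, preferred term and maximum intensity (4.5.2).

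The protocol's renal rule is relative to the participant's own baseline. Among the mitigations for renal changes, Protocol 2.3.1 lists "Monitoring of serum creatinine levels with follow up assessments obtained for any change from baseline" beyond 1.5 times. Protocol 8.2.4.2 makes this operational: "Automatic lab alerts will be sent by the central lab to the investigator and Medical Monitor for increased levels of serum creatinine" above 1.5 times baseline, followed by clinical assessment, examination and repeat tests.

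**The concern.** Renal change is one of the potential risks named for the study drug, and the protocol chose a specific laboratory signal to watch for it. A reader of the study report would expect to see how many participants in each arm gave that signal. As the visible SAP stands, that number does not appear. The creatinine criterion that is programmed uses a different scale, absolute rather than relative, and its results go only to listings. A participant could trigger the central-laboratory alert, be recalled for repeat testing, and then be neither flagged nor counted by size of rise in the report.

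**Working it through.** **Inputs**

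- SAP flag: creatinine above 120 µmol/L (SAP 6.3.1.1). It is stated without derivation, so there is no plan calculation to reproduce.
- Protocol trigger: creatinine above 1.5 × baseline (Protocol 2.3.1 and 8.2.4.2).
- Baseline for chemistry: Day 1 pre-dose (SAP 4.1.2).
- Baseline creatinine and the laboratory's reference range: not given in the documents. I assume baselines from 45 to 90 µmol/L and show the range.

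**Step 1: where the two rules meet.** The trigger equals the flag when 1.5 × b = 120, so b = 120/1.5 = 80 µmol/L.

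**Step 2: what is missed on either side of that point.** For baseline b below 80, values above 1.5b and up to 120 meet the trigger but are not flagged. The fold-rise beyond which the flag fires is 120/b.

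| Baseline b (µmol/L) | Trigger, 1.5b | Unflagged alert-level values | Fold-rise at the flag, 120/b |
|---|---|---|---|
| 45 | 67.5 | >67.5 to 120 | 2.67 |
| 50 | 75 | >75 to 120 | 2.40 |
| 60 | 90 | >90 to 120 | 2.00 |
| 70 | 105 | >105 to 120 | 1.71 |
| 75 | 112.5 | >112.5 to 120 | 1.60 |
| 80 | 120 | none | 1.50 |
| 90 | 135 | none | 1.33 |

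Example: a rise from 60 to 115 is 115/60 = 1.92 times baseline. It triggers the alert and gets no flag. Above 80 the order reverses, and the flag is the more sensitive rule.

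**Step 3: whether another planned display supplies the count.**

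- The normal-range shift table shows that a value crossed the upper limit, but not by what multiple of baseline. A rise from 50 to 78 (78/50 = 1.56) would show no shift at all if the laboratory's upper limit is 78 or more.
- Summaries of change from baseline describe the group and do not count individual fold-rises.
- Adverse event tables include a rise only if it is reported as an event. Protocol 8.2.4.2 allows an alert to end with no action needed, so an alert need not become an event.
- The toxicity grades for creatinine in Protocol 10.7 are multiples of the upper limit of normal, not of baseline.

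**Step 4: how the SAP treats the comparable case.** For QTc, the protocol has a change-from-baseline rule (7.1.2, above 60 msec). The SAP mirrors it with a PCI criterion on increase from baseline (6.3.1.2, 60 msec or more) and a table of maximum increase by category (4.5.3.3). Creatinine also has a baseline-relative rule in the protocol, but neither counterpart appears in the SAP.

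**The case against.** The strongest reply is that PCI is not the endpoint. SAP 6.3.1 presents these limits as flags for potential importance. Clinical significance is the investigator's judgement, and Protocol 8.2.4 tells the investigator to "record any clinically significant changes occurring during the study as an AE". Those events are tabulated by arm. The shift tables give frequencies and percentages for laboratory values, which is literally what the summary measure asks for. Most of this stands. A reader might infer from the listings note that the whole secondary endpoint is left to listings; the documents do not support that, because only the PCI flags are. What remains is that the endpoint list keeps adverse events and clinically significant changes apart, and neither route yields a count of the protocol's creatinine trigger.

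A reader might also infer that the flag fails for anyone with a normal baseline. It does not: the miss needs both a baseline below 80 and a value at or below 120.

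It is tempting, too, to tie the gap to Amendment 5, which moved the exclusion limit from eGFR below 90 to below 60. The direction is against that. At a given age a lower eGFR goes with a higher creatinine, so newly admitted participants tend to lie closer to, or above, the baseline at which the flag catches every trigger-level rise.

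Finally, the detailed displays are in the Output and Programming Specification, which is not public, and parts of the SAP are redacted. The claim can therefore go no further than the visible SAP.

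**Conclusion.** The point holds as a limited reporting gap. No visible SAP table or flag counts participants whose creatinine exceeds 1.5 times baseline, and the absolute flag is no substitute when baseline is below 80 µmol/L. How many participants this could affect cannot be stated, because the documents give no baseline distribution; the table above shows the unflagged band across an assumed range. A rise that stays within the normal range and is not reported as an adverse event would enter no participant-level count in the visible SAP. A rise past the upper limit would be counted as a shift, but without its size.

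A gap in participant safety should not be inferred. The alert, recall and repeat testing in Protocol 8.2.4.2 do not depend on the SAP. Nothing here judges which creatinine threshold is clinically right; the point is that the report should be able to show how often the protocol's own threshold was reached.

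**What to change.** - In SAP 6.3.1.1, add a creatinine criterion of more than 1.5 times the Day 1 pre-dose baseline, matching the alert in Protocol 8.2.4.2. Keep the existing absolute flag.
- In SAP 4.5.3.1, tabulate by arm the number and percentage of participants with any post-baseline value meeting it. Include unscheduled samples, because repeat tests after an alert may fall outside planned visits; SAP 6.3.4 already uses them for worst-case post-baseline values.
- Optionally, tabulate the number and percentage meeting the other PCI criteria where no categorical table exists. QTc is already covered. A split of the creatinine count by baseline eGFR is also optional.
- If the optional tables are taken up, note that 4.5.3.1 says urinalysis values will be flagged, while 6.3.1 shows no urinalysis criteria.

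The cost is one added criterion and one short table, programmed on data already collected. Sites, participants and the protocol's clinical rules are unaffected.
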